9.4.5. Safety Analyses

All safety analyses will be based on the Safety Analysis Set. In general, participants will be analyzed according to their assigned treatment. However, participants assigned to placebo who incorrectly received guselkumab at any time will be analyzed in the guselkumab group; participants assigned to guselkumab who received only placebo during the study will be analyzed in the placebo group.

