1.2. Study Design

This is a randomized, double-blind, placebo-controlled, parallel-group, multicenter study to evaluate the efficacy and safety of guselkumab SC induction therapy in adult participants with moderately to severely active UC defined as a modified Mayo score of 5 to 9, inclusive, Mayo rectal bleeding subscore ≥ 1 and a Mayo endoscopy subscore ≥ 2 . Participants must have demonstrated an inadequate response to or intolerance of conventional (i.e., 6-mercaptopurine (6-MP), azathioprine (AZA), or corticosteroids) or advanced therapy (ADT; i.e., tumor necrosis factor (TNF) α antagonists, vedolizumab, ozanimod, or approved Janus kinase (JAK) inhibitors). An overview over the study design is given in Figure 1.

A target of 399 participants will be enrolled in this study with 133 participants planned per intervention group. Participants who had an inadequate response to or intolerance of advanced therapy (ADT-IR) will comprise a minimum of approximately 40% and a maximum of approximately 50% of the population. Consented participants will be screened for study eligibility within 8 weeks of the Week 0 visit. Eligible participants will be randomized in a 1:1:1 ratio to the following intervention groups:

- Guselkumab CCI at Weeks 0, 4, and 8 followed by guselkumab 200 mg SC q4w through Week 24
- Guselkumab CCl at Weeks 0, 4, and 8 followed by guselkumab 100 mg SC q8w through Week 24
- Placebo SC q4w from Week 0 through Week 24

Participants will be allocated to an intervention group using permuted block randomization stratified by ADT-IR status (Yes/No) and Mayo endoscopy subscore at baseline (moderate [2] or severe [3]).

At weeks 12 and 16, all participants will be evaluated according to predefined rescue criteria as given below. All participants in the placebo group who meet rescue criteria at Week 16 will receive rescue treatment, i.e., guselkumab at Weeks 16, 20, and 24 followed by guselkumab 100 mg SC q8w. Participants randomized to guselkumab who meet rescue criteria at Week 16 will continue their assigned treatment regimen and receive blinded sham rescue with matching placebo SC injections at Weeks 16, 20, and 24.

Rescue criteria are defined as:

• No improvement (i.e., no decrease) in Mayo endoscopy subscore at Week 12, when compared with baseline

AND

• A <2 point improvement (i.e., <2 point decrease) in partial Mayo score at Weeks 12 and 16, when compared with baseline

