All participants who reach the Week 24 visit and are benefiting from study intervention in the opinion of the investigator are eligible for the 72-week study extension. At Week 24, participants entering the 72-week extension period will continue the same treatment regimen they were receiving prior to Week 24 (either the treatment regimen assigned at randomization, or the rescue regimen as described above). The study will be unblinded after the last participant completes the Week 48 assessments and the Week 48 DBL and analyses occur. Upon study unblinding, placebo participants who have not been rescued with guselkumab will be discontinued from study intervention and have a safety follow-up visit. All other participants will continue on guselkumab treatment through Week 96. All participants are to complete the safety follow-up visit 12 weeks after the last dose of study intervention. Only the portion of the extension period prior to Week 48 is within the scope of this document.

Participants who are receiving oral 5-ASA compounds, oral corticosteroids, or conventional immunomodulators (AZA, 6-MP, or MTX) for the treatment of UC at baseline should maintain a stable dose through Week 48; with the exception of oral corticosteroids which require mandatory tapering at Week 12. Enrolled participants should not initiate treatment with these medications from Week 0 to Week 48.

Database locks are planned for Week 24, Week 48, and when the last participant completes the last scheduled assessment as shown in the SoA (Protocol Section 1.3). Additional DBLs may be added as necessary.

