5.2. Participant Dispositions

The number of participants in the following disposition categories through Week 12, Week 24, and Week 48 will be summarized by treatment group and overall based on the Full Analysis Set, the Rescue Analysis Set and the Week 12 Clinical Responder Analysis Set:

- Participants who received study intervention
- Participants who discontinued study intervention
 - Reasons for discontinuation of study intervention
- Participants who terminated study prematurely
 - Reasons for termination of study

Listings of participants will be provided for the following categories:

- All randomized participants
- Participants who discontinued study intervention
- Participants who terminated study prematurely
- Listing of participants with major protocol deviations as given in Appendix 4.

Listings will identify the visits completed and when the study intervention was discontinued or the study was terminated. Further listings regarding intervention compliance are described in Appendix 7.

In addition, the number and percentage of participants who met rescue criteria (according to the IWRS) will be summarized for the full analysis set.

[figure not shown]

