5.6. Safety Analyses

Safety data, including but not limited to, AEs and changes in laboratory assessments, will be summarized. Since vital signs and physical examination data were not collected on the eCRF, no summaries will be provided for vital signs and physical examination findings.

All safety analyses will be based on the Safety Analysis Set. In general, participants will be analyzed according to their assigned treatment. However, participants assigned to placebo who incorrectly received guselkumab at any time will be analyzed in the guselkumab group; participants assigned to guselkumab who received only placebo during the study will be analyzed in the placebo group.

For all continuous safety variables, descriptive statistics by intervention group will include the N, mean, standard deviation, median, minimum, and maximum. Categorical variables will be

summarized by intervention group using frequency counts and percentages. No formal statistical analyses are planned.

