5.6.1. Extent of Exposure

The number and percentage of participants who receive study intervention will be summarized by intervention group.

The cumulative dose and the total number of administrations of study intervention received through Week 12 / Week 24 / Week 48 will be summarized descriptively by intervention group (combined guselkumab SC group, individual guselkumab SC groups, and placebo SC).

In addition, the distribution of participants by study intervention lot through Week 12 / Week 24 / Week 48 based on the Safety Analysis Set will be provided.

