5.6.2. Adverse Events

The verbatim terms used in the CRF by investigators to identify adverse events will be coded using the Medical Dictionary for Regulatory Activities (MedDRA). Any AE occurring at or after the initial administration of study intervention through the final safety follow-up visit is considered to be treatment emergent. If the event occurs on the day of the initial administration of study intervention, and either event time or time of administration are missing, then the event will be assumed to be treatment emergent. If the event date is recorded as partial or completely missing, then the event will be considered to be treatment emergent unless it is known to be prior to the first administration of study intervention based on partial onset date or resolution date. All reported treatment-emergent adverse events will be included in the analysis. For each adverse event, the number and percentage of participants who experience at least 1 occurrence of the given event will be summarized by intervention group.

Summary tables will be provided for treatment-emergent adverse events through Week 24 / Week 48:

- Overall summary of AEs, presenting frequency and type of AEs
- AEs by system organ class (SOC) and preferred term (PT)
- Most frequent AEs by PT
- Serious AEs (SAEs) by SOC and PT
- Related AEs as assessed by the investigator by SOC and PT
- AEs leading to discontinuation of study intervention by SOC and PT
- Any reaction at an SC study intervention injection site that was as recorded as an injectionsite reaction by the investigator on the electronic case report form (eCRF)
- AEs of interest (including special interest)
- Frequency and type of AEs associated with venous thromboembolism (VTE)

The following tables will also be provided through Week 12:

- Overall summary of AEs, presenting frequency and type of AEs
- AEs by system organ class (SOC) and preferred term (PT)
- Serious AEs (SAEs) by SOC and PT
- Related AEs as assessed by the investigator by SOC and PT
- AEs leading to discontinuation of study intervention by SOC and PT
- Any reaction at an SC study intervention injection site that was as recorded as an injectionsite reaction by the investigator on the eCRF

Summaries will be provided by study intervention (combined guselkumab SC group, individual guselkumab SC groups and placebo). In addition to the summary tables, listings will be provided for participants who:

- Had SAEs

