- Had AEs leading to discontinuation of study intervention
- Had SAEs of infection (SOC infections and infestations)
- Had AEs of Opportunistic Infections (Standardized MedDRA Query OPPORTUNISTIC INFECTIONS [SMQ] narrow scope search)
- Had AEs of Tuberculosis (Tuberculous Infections MedDRA High Level Term)
- Had AEs of Malignancy (Malignant Tumours [SMQ] narrow scope search)
- Had AEs associated with major adverse cardiovascular events (MACE), which includes death related to cardiovascular event, nonfatal myocardial infarction, and nonfatal stroke
- Had AEs of drug-induced liver injury (Standardized MedDRA Query DRUG RELATED HEPATIC DISORDERS – COMPREHENSIVE SEARCH [SMQ] narrow scope search)
- Had AEs of VTE
- Had AEs of Anaphylaxis or Serum sickness
- Had an injection-site reaction (any reaction at an SC study intervention injection site that was as recorded as an injection-site reaction by the investigator on the eCRF)
- Had AEs of Suicidal Ideation and Behaviour (Standardized MedDRA Query SUICIDE/SELF-INJURY [SMQ] narrow scope search)
- Deaths

In addition to the tables and listings enumerated above, adverse events will also be summarized as events per 100 subject years of follow-up. This would account for the potential for differences in follow-up times and is applicable to tables of AEs through Week 24 and through Week 48.

Risk difference tables including 95% confidence intervals between placebo and combined guselkumab groups at Week 12 and placebo and individual guselkumab groups at Week 48 will be provided for the following:

• AEs leading to discontinuation

- Serious AEs
- AEs of special interest as defined above

These tables will be provided based on raw cumulative incidence proportions (Weeks 12, 24 and 48), and based on events per 100 subject years of follow-up (Week 48 only).

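### The SAP has no safety rule, column or cut for placebo participants correctly rescued with guselkumab, so by default their post-rescue data count as placebo

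*SAP*

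**What the plan says.** **Rescue is part of the design.** Under SAP 1.2, placebo participants who meet the rescue criteria receive "guselkumab at Weeks 16, 20, and 24 followed by guselkumab 100 mg SC q8w".

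**Safety grouping.** SAP 5.6 states: "In general, participants will be analyzed according to their assigned treatment". It then gives two exceptions, and protocol 9.4.5 has the same rule. For the placebo arm the exception reads: "participants assigned to placebo who incorrectly received guselkumab at any time will be analyzed in the guselkumab group". The other concerns guselkumab participants who received nothing but placebo.

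**Columns.** Exposure through Weeks 12, 24 and 48 (SAP 5.6.1) "will be summarized descriptively by intervention group (combined guselkumab SC group, individual guselkumab SC groups, and placebo SC"). For adverse events (SAP 5.6.2): "Summaries will be provided by study intervention (combined guselkumab SC group, individual guselkumab SC groups and placebo"). The same section adds that "adverse events will also be summarized as events per 100 subject years of follow-up", and calls for risk differences between placebo and guselkumab groups. Laboratory changes through Week 48 (SAP 5.6.3.1) are shown for the individual guselkumab groups and placebo.

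**Window and baseline.** An adverse event is treatment emergent from the first dose of study intervention up to the last safety follow-up, and all such events are counted. Laboratory baseline is the last value before the first dose of study agent.

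**The concern.** The exception covers guselkumab given to a placebo participant by mistake. A participant rescued according to protocol received it correctly, so the default applies and the data stay under placebo. Nothing in SAP 5.6 or protocol 9.4.5 says otherwise, and no column exists to hold them.

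The Week 24 and Week 48 tables are the plan's only controlled safety display beyond Week 12. In them, an event after a planned guselkumab dose would be counted under placebo, and the placebo exposure row would contain guselkumab doses. The as-assigned contrast is legitimate as a comparison of guselkumab with placebo plus protocol rescue, but no table would say that this is what it shows. Subject-year rates adjust for length of follow-up, not for a change of treatment.

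**Working it through.** **Text check: where the plan deals with rescue**

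| Output | Handling of rescue |
|---|---|
| Primary and secondary efficacy (SAP Table 6) | Intercurrent event 4, composite strategy |
| Time-to-event endpoints (SAP 5.5.4) | Censored at that event |
| PK (SAP 5.7.1.1) | Grouped by intervention actually received |
| PK and Immunogenicity Analysis Sets (SAP Table 4) | Keyed to the first guselkumab dose |
| Rescue Analysis Set | Disposition, baseline, medications and six descriptive efficacy or biomarker endpoints; no safety output |
| Adverse events, exposure, laboratory tests (SAP 5.6) | None |

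Rescue is handled in most places, but not in the safety section.

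**Size**

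The plan gives no figure on this point to reproduce. Inputs:
- Placebo arm: 133 planned (SAP 1.2).
- Rescue starts at Week 16; tables close at Weeks 24 and 48.
- Rescue fraction r is not in the documents. Assumed 10% to 50%, so n = 133r = 13.3 to 66.5 participants.
- Full follow-up is assumed, with 365.25 days per year.

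*Share of placebo-column time after rescue* = r × (W − 16)/W:
- Week 24: r × 8/24 = 0.033 to 0.167.
- Week 48: r × 32/48 = 0.067 to 0.333.

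*Subject-years:*
- Week 24: total 133 × 24 × 7/365.25 = 61.2; after rescue n × 8 × 7/365.25 = 2.0 to 10.2.
- Week 48: total 133 × 48 × 7/365.25 = 122.3; after rescue n × 32 × 7/365.25 = 8.2 to 40.8.

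A 52-week year gives totals of 61.4 and 122.8; the shares do not change.

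*Guselkumab dosing visits in the placebo exposure row:*
- Through Week 24: 2n = 26.6 to 133 (Weeks 16 and 20), or 3n = 39.9 to 199.5 if the Week 24 dose is counted.
- Through Week 48: 5n = 66.5 to 332.5 (Weeks 16, 20, 24, 32 and 40), or 6n = 79.8 to 399 with Week 48.

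The Week 48 count assumes that the first q8w dose after rescue comes 8 weeks after Week 24, as Arm B's first q8w dose at Week 16 follows its Week 8 dose (protocol 6.1).

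*Laboratory baseline.* For a rescued participant, the value before the first dose of study agent precedes the first placebo dose, at least 16 weeks before any guselkumab.

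**The case against.** **Placement under placebo is an inference.** The default is qualified as general, adverse events are summarised by study intervention, and the documents do not include table shells, where a rescue column might exist. Treatment assigned could also be read to include rescue, since SAP 1.2 describes the regimen continued at Week 24 as "either the treatment regimen assigned at randomization, or the rescue regimen as described above". It is true that the SAP does not state the placement outright. But the exception itself refers to participants assigned to placebo in the sense of the randomised arm, and even the wider reading leads nowhere, because no safety column exists for the rescue regimen.

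**Other outputs help.** Disposition, including reasons for stopping study intervention, is "summarized by treatment group and overall based on the Full Analysis Set, the Rescue Analysis Set and the Week 12 Clinical Responder Analysis Set". The number meeting rescue criteria is reported. Adverse event listings show individual cases. Participants positive for antibodies are listed with dose and injection-site reactions. These limit the problem, but none gives event rates, denominators or exposure split by treatment.

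**The stakes are limited.** No formal safety test is planned, Week 12 tables precede rescue, and the as-assigned contrast is valid. All of this stands.

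**The size is illustrative.** This also stands. The SAP version history says the Rescue Analysis Set was warranted by the number rescued, but that set includes guselkumab participants on sham rescue, so it does not bound r. Entry to the extension requires benefit in the investigator's judgement, so retention may differ between rescued and non-rescued participants. The Week 48 share could lie on either side of 7% to 33%.

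**Conclusion.** The concern holds. The plan states no rule for placebo participants correctly rescued with guselkumab, and its default puts their post-rescue safety data in an unlabelled placebo column at Weeks 24 and 48. The missing rule is certain from the text; the placement follows from the default. The size rests on the assumed 10% to 50% rescue fraction and full follow-up: 3% to 17% of placebo-column time through Week 24 and 7% to 33% through Week 48.

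No effect on event rates or risk differences is claimed. Rescued participants are selected non-responders, so the net direction is uncertain. No test, power figure or success criterion changes. This should be fixed before the Week 24 and Week 48 safety tables are produced.

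**What to change.** State the rule for correctly rescued placebo participants in SAP 5.6, with matching words in protocol 9.4.5. The protocol leaves analysis detail to the SAP, so the SAP text does the work; the protocol edit keeps the two aligned. For safety tables that extend past Week 16:

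1. Split placebo-arm events (by onset date), laboratory values, doses and follow-up time at the first rescue dose of guselkumab.
2. Show *Placebo* up to that dose and *Placebo to guselkumab* from it, with subject-year rates for both.
3. Name the baseline for laboratory changes, shifts and worst grade in the second column, for example the last value before the first rescue dose. Otherwise the pre-placebo value applies.
4. Keep the as-randomised Week 24 and Week 48 risk differences, labelled *guselkumab versus placebo with protocol rescue*. SAP 5.6.2 names group contrasts only for Weeks 12 and 48 but then lists Week 24 as well, so the Week 24 contrast should be spelled out. A contrast censored at rescue is optional.

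**Cost.** Wording, plus programming for the adverse event, rate, exposure and laboratory tables past Week 16. The pre-rescue placebo rate loses precision. With a constant event rate, its standard error grows by 1/√(1 − share) − 1: 0.017 to 0.095 (about 2% to 10%) through Week 24 and 0.035 to 0.225 (about 4% to 22%) through Week 48, under the same assumptions. After Week 16 the *Placebo* column also holds only participants who were not rescued, so its later rate comes from a selected group. That is why the as-randomised contrast should stay.

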5.6.1. Extent of Exposure

The number and percentage of participants who receive study intervention will be summarized by intervention group.

The cumulative dose and the total number of administrations of study intervention received through Week 12 / Week 24 / Week 48 will be summarized descriptively by intervention group (combined guselkumab SC group, individual guselkumab SC groups, and placebo SC).

In addition, the distribution of participants by study intervention lot through Week 12 / Week 24 / Week 48 based on the Safety Analysis Set will be provided.

5.6.2. Adverse Events

The verbatim terms used in the CRF by investigators to identify adverse events will be coded using the Medical Dictionary for Regulatory Activities (MedDRA). Any AE occurring at or after the initial administration of study intervention through the final safety follow-up visit is considered to be treatment emergent. If the event occurs on the day of the initial administration of study intervention, and either event time or time of administration are missing, then the event will be assumed to be treatment emergent. If the event date is recorded as partial or completely missing, then the event will be considered to be treatment emergent unless it is known to be prior to the first administration of study intervention based on partial onset date or resolution date. All reported treatment-emergent adverse events will be included in the analysis. For each adverse event, the number and percentage of participants who experience at least 1 occurrence of the given event will be summarized by intervention group.

Summary tables will be provided for treatment-emergent adverse events through Week 24 / Week 48:

- Overall summary of AEs, presenting frequency and type of AEs
- AEs by system organ class (SOC) and preferred term (PT)
- Most frequent AEs by PT
- Serious AEs (SAEs) by SOC and PT
- Related AEs as assessed by the investigator by SOC and PT
- AEs leading to discontinuation of study intervention by SOC and PT
- Any reaction at an SC study intervention injection site that was as recorded as an injectionsite reaction by the investigator on the electronic case report form (eCRF)
- AEs of interest (including special interest)
- Frequency and type of AEs associated with venous thromboembolism (VTE)

The following tables will also be provided through Week 12:

- Overall summary of AEs, presenting frequency and type of AEs
- AEs by system organ class (SOC) and preferred term (PT)
- Serious AEs (SAEs) by SOC and PT
- Related AEs as assessed by the investigator by SOC and PT
- AEs leading to discontinuation of study intervention by SOC and PT
- Any reaction at an SC study intervention injection site that was as recorded as an injectionsite reaction by the investigator on the eCRF

Summaries will be provided by study intervention (combined guselkumab SC group, individual guselkumab SC groups and placebo). In addition to the summary tables, listings will be provided for participants who:

- Had SAEs
- Had AEs leading to discontinuation of study intervention
- Had SAEs of infection (SOC infections and infestations)
- Had AEs of Opportunistic Infections (Standardized MedDRA Query OPPORTUNISTIC INFECTIONS [SMQ] narrow scope search)
- Had AEs of Tuberculosis (Tuberculous Infections MedDRA High Level Term)
- Had AEs of Malignancy (Malignant Tumours [SMQ] narrow scope search)
- Had AEs associated with major adverse cardiovascular events (MACE), which includes death related to cardiovascular event, nonfatal myocardial infarction, and nonfatal stroke
- Had AEs of drug-induced liver injury (Standardized MedDRA Query DRUG RELATED HEPATIC DISORDERS – COMPREHENSIVE SEARCH [SMQ] narrow scope search)
- Had AEs of VTE
- Had AEs of Anaphylaxis or Serum sickness
- Had an injection-site reaction (any reaction at an SC study intervention injection site that was as recorded as an injection-site reaction by the investigator on the eCRF)
- Had AEs of Suicidal Ideation and Behaviour (Standardized MedDRA Query SUICIDE/SELF-INJURY [SMQ] narrow scope search)
- Deaths

In addition to the tables and listings enumerated above, adverse events will also be summarized as events per 100 subject years of follow-up. This would account for the potential for differences in follow-up times and is applicable to tables of AEs through Week 24 and through Week 48.

Risk difference tables including 95% confidence intervals between placebo and combined guselkumab groups at Week 12 and placebo and individual guselkumab groups at Week 48 will be provided for the following:

• AEs leading to discontinuation

- Serious AEs
- AEs of special interest as defined above

These tables will be provided based on raw cumulative incidence proportions (Weeks 12, 24 and 48), and based on events per 100 subject years of follow-up (Week 48 only).

